3.1.3 Part 3: Combination Dose Expansion

The Combination Dose Expansion part of the study will be separate from the Combination Dose Finding part and will evaluate the safety and efficacy of ANV419 in combination with pembrolizumab (Arm B) or ipilimumab (Arm C). This Combination Dose Expansion part will consist of 2 stages. In Stage 1, 12 patients will be randomized by interactive response technology (IRT) into each arm. At the end of this stage, an interim analysis will be performed to assess continuation of treatment arms into Stage 2 (see Table 8). In Stage 2, eligible patients will be randomized to the remaining treatment arms, determined at the interim analysis. Recruitment will continue until 25 patients have been randomized to a treatment arm.

 Table 8.
 Continuation Decision Rules for Combination Dose Expansion Part

	Discontinue if the	Discontinue Criterion in	Continue if the Number
Treatment Arm Accrual	Number of Responses is	Terms of ORR	of Responses is at Least
Stage 1 (n=12) ≤2		Observed ORR <20%	3
ORR = objective response rate.			

Dosing for ANV419 in the combination arms (Arms B and C) in the Combination Dose Expansion part will be based on the RP2Ds for ANV419 determined in the Combination Dose Finding part, ie, the RP2D for ANV419 when administered in combination with pembrolizumab (hereinafter, RP2D[p]) and the RP2D for ANV419 when administered in combination with ipilimumab (hereinafter, RP2D[i]).

Treatment with ANV419 in combination with pembrolizumab can continue for 24 months within the current Protocol in the absence of disease progression or unacceptable toxicity.

Treatment with ANV419 in combination with ipilimumab can continue up to a maximum of 4 cycles, per the approved label (United States Prescribing Information and Summary of Product Characteristics). If ipilimumab-related AEs occur, ipilimumab can be discontinued at any time. Once a patient has completed the maximum of 4
once a patient has completed the maximum of 1
3.1.4 Dose-Limiting Toxicity Criteria (Applicable to Combination Dose Finding Part Only)
A DLT is defined as any of the treatment-emergent AEs (TEAEs) listed below, as defined by the National Cancer Institute Common Terminology Criteria for Adverse Events (NCI CTCAE) version 5.0, occurring during the DLT period (
DLT definitions are the following:
DL1 definitions are the following.

An SRC will be convened, comprised of enrolling study Investigators, Medical Monitor, and the Sponsor Medical Director or designee. All potentials DLTs will be reviewed by the SRC for a final determination and for the SRC to make recommendations regarding the study. The SRC will also

consider AEs, particularly high-grade toxicities that may have occurred in patients in any treatment arm (even beyond the DLT period), when making decisions/recommendations to proceed with the study. The SRC will provide recommendations for study drug dosing and alternative dosing regimens as appropriate, not exceeding a 3-fold increment from one dose level to the next. The maximum dose level explored will not exceed the dose of ANV419 monotherapy studied in the ongoing ANV419-001 study. Near the end of dose escalation, the statistician will also contribute to dose escalation recommendation, using the BOIN design, to select the MTD/RP2D.

After completion of the DLT period for each cohort, intra-patient dose escalation is permitted with approval of the Investigator and provided the following criteria have been met:

- The patient has completed at least 1 treatment cycle;
- The DLT assessment of the dose level to which the patient will be dose-escalated is complete and determined to be safe by the SRC;
- The patient did not experience any AEs related to study drug(s) >Grade 1 at the dose level prior to escalation; and
- The patient has not required any dose reduction.

3.2 Stopping Rules

Treatment of individual patients may be stopped under defined circumstances as outlined in Section 4.4.

3.3 Safety Review Committee

An SRC will be established to monitor safety aspects of the trial and make recommendations to Anaveon and Medpace about trial conduct to ensure patient safety and scientific validity.

The SRC Charter will further describe membership and responsibilities of the SRC.

3.4 Study Indication(s)

ANV419 is being developed for treatment of unresectable or metastatic CM following at least 1 line of standard of care immunotherapy, including an anti-PD-1 and/or anti-PD-L1 antibody.

4 SELECTION AND WITHDRAWAL OF PATIENTS

Population

Patients with unresectable or metastatic CM with measurable disease, whose disease has progressed following or on at least 1 line of standard of care immunotherapy (on anti-PD-1, anti-PD-L1, and/or CTLA-4 antibody treatment).

4.1 Inclusion Criteria

Patients who meet all of the following criteria will be eligible to participate in the study:

- 1. Must provide written informed consent for the study;
- 2. Must be able to comply with the Protocol as judged by the Investigator;
- 3. Are \geq 18 years of age on day of signing informed consent;
- 4. Have histologically confirmed Stage 3 (unresectable) or Stage 4 (metastatic) CM, as per the American Joint Committee on Cancer staging system, eighth edition;
- 5. Have documented radiological progression on prior systemic therapy;
- 6. Have previously received anti-PD-1/L1 as monotherapy or in combination. A maximum of 2 prior lines of systemic therapy is allowed for BRAF wild-type disease and a maximum of 3 prior lines of systemic therapy is allowed for BRAFV600 positive disease;

Note: Adjuvant treatment is considered as a line of therapy only if patient experienced relapse/progression on therapy or within 6 months from adjuvant therapy completion;

- 7. Have measurable disease based on RECIST;
- 8. Have a performance status of 0 or 1 on the ECOG Performance Status;
- 9. Have adequate organ functions as defined in Table 9:

Table 9. Adequate Organ Function Laboratory Values

System	Laboratory Value
Hematological	
ANC	≥1500/μL
Platelets	≥100,000/μL
Hemoglobin	≥9 g/dL or ≥4.96 mmol/L
Renal	
Measured or calculated ¹ CrCl (GFR can also	
be used in place of CrCl)	≥30 mL/min
Hepatic	
	\leq 1.5 × ULN OR \leq 1.5 × ULN for patients with total bilirubin
	levels >1.5 × ULN; direct bilirubin \leq 1.5 × ULN for patients with
Serum total bilirubin OR direct bilirubin	Gilbert's syndrome
AST (SGOT) or ALT (SGPT)	$\leq 2.5 \times \text{ULN } \underline{\text{OR}} \leq 5 \times \text{ULN for patients with liver metastases}$
Albumin	>2.5 g/dL

^{1.} CrCl should be calculated per Cockcroft-Gault equation.

ALT = alanine aminotransferase; ANC = absolute neutrophil count; AST = aspartate aminotransferase; CrCl = creatinine clearance; GFR = glomerular filtration rate; SGOT = serum glutamic oxalacetic transaminase; SGPT = serum glutamic pyruvic transaminase; ULN = upper limit of normal.

- 10. Female patients of childbearing potential must have a negative serum pregnancy test at the Screening Visit and a negative (urine or serum) pregnancy test within 72 hours prior to study Day 1. If the urine test is positive or cannot be confirmed as negative, a serum pregnancy test will be required and must be negative for the patient to be eligible;
- 11. Female patients who are not postmenopausal, and who have not undergone surgical sterilization, must agree to use highly effective methods of contraception during the treatment period and for 6 months after the last dose of study drug. They must also agree not to donate eggs (ova, oocytes) during the same timeframe; and
- 12. Male patients with partners of childbearing potential must agree to use highly effective methods of contraception and barrier contraception (condom) during the treatment period and for 6 months after the last dose of study drug. They must also agree not to donate sperm during the same timeframe.

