- 5 responses in 20 to 27 patients.

Combination Dose Finding part

The Combination Dose Finding part will employ BOIN^a to find the MTD/RP2D of Arm B (ANV419 in combination with pembrolizumab) and Arm C (ANV419 in combination with ipilimumab). For each arm, the following assumptions have been predefined for the dose escalation:

- Target DLT rate of 25%;
- Maximum of 25 patients;
- Maximum of 9 patients treated at the same dose level; and
- Maximum of 5 dose levels defined in TS5 to be tested.

Patients will be enrolled and treated in cohorts of 3 patients (at least). Up to 50 patients in total will be enrolled for the Combination Dose Finding part.

Combination Dose Expansion part (efficacy analysis)

The sample size calculation is based on a Simon's 2-stage^a design and ensures that under all possible distributions of patients to the 2 treatment arms, there is at least 80% power to correctly detect an ORR >40% and at most a Type I error rate of 10% of rejecting a null hypothesis that ORR <20%. This results in a sample size of 12 patients randomized to each treatment arm in

Stage 1, followed by 13 additional patients randomized during Stage 2: a total of 25 patients per arm at the end of Stage 2.

SITES: Approximately 30 sites in the United States of America and Europe

SPONSOR:

Anaveon AG [name] [name] [name] Switzerland

[contact]

a. Simon R. Optimal two-stage designs for phase II clinical trials. Control Clin Trials. 1989;10(1):1-10.

TABLE OF CONTENTS

Si	gnatur	e Page		2	
In	vestiga	ator Ag	reement	3	
Sy	nopsis	S		4	
Та	ble of	Conten	its	23	
Li	st of T	ables		28	
Li	st of F	igures.		29	
List of Abbreviations and Definition of Terms					
1	Intro	duction	and Background Information	33	
	1.1	Immu	notherapy	33	
	1.2		eous Melanoma		
	1.3	ANV4	19	35	
		1.3.1	Nonclinical Pharmacology	35	
		1.3.2	Nonclinical Pharmacokinetics	36	
		1.3.3	Toxicology		
		1.3.4	Clinical Experience		
	1.4	Ration	nale	39	
	1.5	Risk/I	Benefit	40	
2		-	tives and Endpoints		
3	Stud	y Descr	iption	45	
	3.1	Summ	ary of Study Design		
		3.1.1	Part 1: Monotherapy Dose Expansion		
		3.1.2	Part 2: Combination Dose Finding		

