7.7 Clinical Laboratory Assessments

Clinical laboratory assessments (urinalysis, coagulation, chemistry, serology, endocrinology, and hematology) will be performed locally as indicated in Appendix A and will include the laboratory analytes presented in Appendix B. Patients found to have treatment-emergent laboratory toxicity of Grades 3 or 4 will be monitored at least weekly until resolution. Urinalysis may be done by dipstick or microscopy.

If applicable for logistical reason, clinical laboratory assessments can be performed within 24 hours from ANV419 administration.

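### The haemoglobin entry limit pairs 9 g/dL with 4.96 mmol/L, but 4.96 mmol/L is about 8.0 g/dL, so patients between the two values can pass or fail depending on the unit used

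*Protocol*

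**What the plan says.** Inclusion criterion 9 in Protocol Section 4.1 reads "Have adequate organ functions as defined in Table 9". In that table the haemoglobin row is "≥9 g/dL or ≥4.96 mmol/L". Table TS4 in the Synopsis prints the same pair. Neither table gives a conversion factor for haemoglobin, a footnote to the row, or a reason for having two different limits.

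Two other statements bear on how the criterion works in practice. Protocol Section 7.7 says that clinical laboratory assessments, which include haematology, "will be performed locally as indicated in Appendix A and will include the laboratory analytes presented in Appendix B". The Synopsis plans for "Approximately 30 sites in the United States of America and Europe".

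**The concern.** A limit printed in two units should be one limit. If the two numbers do not convert into each other, there is a band of haemoglobin values in which a patient meets one figure and fails the other, and the protocol does not say which governs.

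This is an eligibility threshold with a safety purpose, in a Phase 1/2 study with at most 15 patients per monotherapy arm. If sites apply it differently, patients with the same haemoglobin are treated differently at entry, and a few admissions under the looser figure could change the baseline profile of a small arm. It also becomes unclear whether enrolling a patient in the band is a protocol deviation, and SAP Section 3.3.2 plans to classify and summarise deviations.

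**Working it through.** **Inputs from the documents.** The g/dL limit is 9 and the mmol/L limit is 4.96 (Protocol Table 9, repeated in Table TS4).

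**Assumed input.** The conversion factor is f = 10 / M × 1000, in mmol/L per g/dL, where M is the molar mass in g/mol. For the haemoglobin monomer, M is about 16,114, so f = 10 / 16,114 × 1000 = 0.6206. Usual rounded factors run from 0.620 to 0.625.

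**Can the 4.96 be reproduced from 9 g/dL?**

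| Factor | 9 g/dL in mmol/L (9 × f) | 4.96 mmol/L in g/dL (4.96 / f) |
|---|---|---|
| 0.620 | 5.58 | 8.00 |
| 0.6206 | 5.585 | 7.99 |
| 0.625 | 5.625 | 7.94 |

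It cannot. With f = 0.6206 the gap is 9 − 7.99 = 1.01 g/dL, or 5.585 − 4.96 = 0.625 mmol/L. Over the range of factors the gap is 1.00 to 1.06 g/dL.

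**Could another basis explain the pair?** On the tetramer basis (M about 64,458, f about 0.155), 9 g/dL is 1.40 mmol/L and 4.96 mmol/L is 32 g/dL, which is further off. For the two figures to agree, f would have to be 4.96 / 9 = 0.551, that is M = 9 × 10 / 4.96 × 1000 = 18,145 g/mol, which fits neither basis.

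**What does 4.96 correspond to?** 8 × 0.62 = 4.96 exactly. The mmol/L figure is therefore what an 8 g/dL limit would give. The documents do not show whether 8 or 9 g/dL was intended.

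**Who is affected?** With f = 0.6206:

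| Haemoglobin (g/dL) | In mmol/L | Meets 9 g/dL | Meets 4.96 mmol/L |
|---|---|---|---|
| 8.0 | 4.96 | no | yes |
| 8.3 | 5.15 | no | yes |
| 8.5 | 5.28 | no | yes |
| 8.9 | 5.52 | no | yes |

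The affected band runs from about 8.0 to just below 9.0 g/dL.

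**What the 'or' does.** There are two readings:

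1. As the same limit in two units, a site applies the figure in its own laboratory's unit. Patients in the band are then excluded where g/dL is reported and admitted where mmol/L is reported.
2. As a literal either/or, meeting the looser figure is enough. Every site then has an effective limit of about 8.0 g/dL, and the 9 g/dL figure does nothing.

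Under neither reading does the criterion enforce the 9 g/dL that it prints.

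**The case against.** The arithmetic is not in dispute. The case on the other side concerns the consequences.

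- **A literal reading is uniform.** If 'or' means either figure suffices, eligibility does not depend on the site's unit. That is correct, but the 9 g/dL figure is then redundant and the real limit is about 1 g/dL lower than a reader would take it to be. This reading changes the form of the error without removing it.
- **The regional effect is not shown.** The protocol says that laboratory work is local and that sites are in the USA and Europe, but not which unit any laboratory reports. This stands: a difference between regions is a possibility, not an established fact, and the number of patients affected is unknown.
- **The clinical weight is limited.** In the earlier ANV419-001 study, drug-related anaemia was reported in 2 of 34 patients (Protocol Appendix F, Table 25), and anaemia is absent from the list of events of Grade 3 or higher (Section 1.3.4, Table 1). Haemoglobin is monitored on study, and exclusion criterion 17 lets the investigator keep out a patient with a worrying laboratory abnormality. These points limit the harm. They do not tell a site which figure to apply.
- **The trial has stopped.** SAP Section 1 records the decision of 27 February 2024 to stop at the end of Part 1. Correcting the tables would now change no enrolment. This also stands, and it shifts the practical remedy towards reporting.

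**Conclusion.** The concern holds. The two haemoglobin figures differ by about 1.0 g/dL (0.63 mmol/L), in both places where the limit appears, and nothing else in the protocol corrects them. The conclusion rests on a conversion factor from outside the documents, but the mismatch is present for every factor from 0.620 to 0.625 and on the tetramer basis.

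The consequence is an ambiguous eligibility threshold for patients at about 8.0 to just below 9.0 g/dL. That eligibility varies by site follows from reading the figures as unit alternatives, which is the natural reading, and from both units being in use, which the documents allow but do not confirm. Sample size, error rates and the primary response-rate analysis are not affected. It is worth correcting because it is a wrong threshold in an inclusion criterion, but it does not threaten the trial's conclusions.

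**What to change.** State one limit in both units, identically in Table 9 and Table TS4: either 9 g/dL with 5.59 mmol/L, or 8 g/dL with 4.96 mmol/L. The sponsor must say which was intended, since the documents do not settle it.

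The edit is one figure in two tables. Because it alters an eligibility criterion, it would go through the amendment review and approval described in Protocol Section 11.1. While the trial was still planned to continue, it could have been included in the substantial amendment that Section 3.1.2 already required before Part 2.

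As enrolment has ended, the useful step now is to list Part 1 patients whose baseline haemoglobin was between about 8.0 and 9.0 g/dL, and to state in the study report which limit was applied and whether such patients count as eligibility deviations. SAP Section 3.8.2 already converts laboratory values to standard units, so this needs one short listing and no new data.

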4.2 Exclusion Criteria

Patients who meet any of the following criteria will be excluded from participation in the study:

- 1. Have received investigational agent (including investigational device) within 4 weeks or an interval of 5 half-lives of the respective investigational agent prior to study Day 1, whichever is longer, with the exclusion of an anti-PD-1/anti-PD-L1 antibody given as either a single agent or non-CTLA-4 antibody containing combination (eg, anti-lymphocyte-activation gene 3 antibody);
- 2. Have a known hypersensitivity to ANV419 or to any of the excipients, such as sucrose, histidine or polysorbate 80. For combination arms only: Have hypersensitivity to pembrolizumab or ipilimumab or any of their excipients;
- 3. For combination arms only: Have previously discontinued ipilimumab, pembrolizumab, or any other PD-1/PD-L1 inhibitors due to unacceptable drug-related toxicity (defined as toxicities that required second line immunosuppression, ie, not controlled by steroids alone);
- 4. Have an LDH level of $\geq 2 \times$ upper limit of normal;
- 5. Have not recovered (ie, ≤Grade 1 or at baseline with the exception of alopecia or fatigue [up to Grade 2 allowed]) from AEs resulting from prior immunotherapies. Patients who have autoimmune AEs controlled by replacement therapy (ie, hypothyroidism) due to previous treatment are eligible provided replacement therapy has been initiated and toxicity has returned to Grade 1;
- 6. Have not recovered (ie, ≤Grade 1 or at baseline) from toxicities due to a previously administered prior chemotherapy, targeted small molecule therapy, or radiation therapy;
 - Note: If the patient received major surgery, they must have recovered adequately from the toxicity and/or complications from the intervention prior to starting study drug. Major surgery is defined as any surgery requiring entrance into a body cavity (eg, chest, abdomen, or brain), organ removal, normal anatomy alteration, or joint replacement. Minor surgery is defined as any surgery in which skin, mucosa, or connective tissue sections are altered (eg, biopsy, cataract, endoscopic procedures, etc).
- 7. Have been diagnosed with uveal/ocular or mucosal melanoma;

- 8. Have a known additional malignancy (including all in-situ carcinoma) that is progressing or requires active treatment within ≤2 years prior to enrollment. Exceptions include basal cell carcinoma of the skin or squamous cell carcinoma of the skin that have undergone potentially curative therapy or in situ cervical cancer or patients who completed cancer-directed therapy and have no evidence of disease;
- 9. Have active central nervous system metastases and/or carcinomatous meningitis. Patients with previously treated brain metastases may participate provided they are stable (without evidence of progression by imaging for at least 4 weeks prior to study Day 1 and any neurologic symptoms have returned to baseline or have been stable for at least 7 days), have no evidence of new or enlarging brain metastases, and are not using steroids for at least 7 days prior to study drug. This exception does not include carcinomatous meningitis which is excluded regardless of clinical stability;
- 10. Have a diagnosis of immunodeficiency or is receiving immunosuppressive therapy within 7 days prior to study Day 1;
- 11. Are receiving systemic steroid >10 mg of prednisone daily or equivalent or any other immunosuppressive medication at any dose level. Local steroid therapies (eg, otic, ophthalmic, intra-articular, or inhaled medications) are acceptable;
- 12. Have an active autoimmune disease that has required systemic treatment in the past 2 years (ie, with use of disease modifying agents, corticosteroids, or immunosuppressive drugs). Replacement therapy (eg, thyroxine, insulin, or physiologic corticosteroid replacement therapy for adrenal or pituitary insufficiency, etc) is not considered a form of systemic treatment;
- 13. Have evidence of active, non-infectious pneumonitis;
- 14. Have active (measurable) and uncontrolled (unresponsive to current therapy) infectious disease (bacterial, fungal, viral, or protozoic);
- 15. Have a history of an acute coronary event (eg, myocardial infarction) within 3 months prior to study Day 1, uncontrolled and symptomatic coronary artery disease or congestive heart failure New York Heart Association Class III/IV;
- 16. Have an average QTcF interval >470 msec at Screening;
- 17. Have a history or current evidence of any condition, therapy, or laboratory abnormality that might confound the results of the study, interfere with the patient's participation for the full duration of the study, or it is not in the best interest of the patient to participate, in the opinion of the treating Investigator;
- 18. Have known psychiatric or substance abuse disorders that would interfere with cooperation with the requirements of the study;
- 19. Are pregnant or breastfeeding, or expecting to conceive or father children within the projected duration of the study, starting with the Screening Visit through 6 months after the last dose of study drug;
- 20. Are known to be human immunodeficiency virus (HIV) positive (or tests positive for HIV 1 or 2 at Screening), unless the following criteria are met:
 - a. CD4+ lymphocyte count >350 μ L;

- b. Had no history of acquired immunodeficiency syndrome (AIDS)-defining opportunistic infections within the past 12 months;
- c. Have been on established anti-retroviral therapy for at least 4 weeks; and
- d. Have an HIV viral load of <400 copies/mL prior to study Day 1.

Note: Patients on strong cytochrome P450 (CYP)3A4 inhibitors or strong CYP3A4 inducers must be switched to an alternate effective anti-retroviral therapy regimen prior to study treatment or are excluded if regimen prior to study Day 1 cannot be altered.

21. Have uncontrolled hepatitis B infection or hepatitis C infection;

Note: Patients with hepatitis B (positive hepatitis B surface antigen) who have controlled infection (serum hepatitis B virus DNA by polymerase chain reaction that is below the limit of detection and receiving anti-viral therapy for hepatitis B) are permitted. Patients with controlled infections must undergo periodic monitoring of hepatitis B virus DNA.

Note: Patients with hepatitis C (positive hepatitis C virus antibody) who have controlled infection (undetectable hepatitis C virus RNA by polymerase chain reaction either spontaneously or in response to a successful prior course of anti-hepatitis C virus therapy) are permitted.

22. Have received a live vaccine within 30 days of study Day 1; or

Note: Seasonal influenza vaccines for injection are generally inactivated flu vaccines and are allowed; however, intranasal influenza vaccines (eg, Flu-Mist®) are live attenuated vaccines, and are not allowed.

23. For combination arms only: Have received solid organ or hematopoietic stem cell transplant.

